9.7.3.3 Statistical Methods for Analysis of Effectiveness Variables

The simple percentage of patients achieving SVR12 will be calculated and an exact two-sided 95% confidence interval (CI) of the percentage will be computed based on the Clopper-Pearson method.

Corresponding methods will be used for other response rates (EoT response rate, relapse rate, viral breakthrough). The relapse rates will be estimated in patients of the CP analysis groups with EoT response and sufficient HCV RNA measurements post-treatment. Viral breakthrough rates will be estimated in all patients of the CP analysis groups, who have at least one undetectable HCV RNA measurement on-treatment and at least one on-treatment or EoT measurement thereafter.

Univariate and multiple logistic regression (MLR) methods will be used to investigate the impact of the following explanatory covariates on SVR12:

- Key demographic information
- Mode of CHC infection
- HCV RNA level at baseline
- Most recent stage of liver fibrosis
- HCV genotype and subtype (if available)
- Type of treating institute
- Liver and/or CHC related co-morbidities
- Key clinical chemistry and hematology laboratory variables at baseline
- In treatment experienced patients only:
 - Most recent prior treatment for CHC
 - Outcome of most recent prior CHC treatment

Further details and additional covariates will be specified in the SAP.

These analyses will be of exploratory nature, data driven, and will be repeatedly performed for various CP Analysis Groups, since not each covariate might be

predictive in each patient group. Furthermore, the fact that treatment regimens will differ in the various patient groups has to be taken into account, when selecting the patient groups for each MLR analysis. Backward selection procedures will be applied to generate the final MLR models which consider only covariates in the selection procedure with a p-value <0.25 in the corresponding univariate logistic regression analysis. A p-value <0.05 will be used for the covariates to stay in the model in a backward elimination step. Logistic regression methods will also be used to investigate the impact of treatment adherence on SVR12.

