## Core Population with Sufficient Follow-up [CPSFU {12, 24}]

In addition, the core population with sufficient follow-up data regarding SVR12 or SVR24, respectively, is defined as all CP patients,

- who have evaluable HCV RNA data ≥70 days or >126 days, respectively, after the last actual dose of the ABBVIE REGIMEN
- or a HCV RNA value ≥50 IU/mL at the last measurement
- or had HCV RNA <50 IU/mL at the last measurement, but no HCV RNA measurement ≥70 days or >126 days, respectively, after the last actual dose of the ABBVIE REGIMEN due to reasons related to safety (e.g. dropped out due to adverse event) or virologic failure (e.g. virologic failure such as relapse is reported in the electronic case report form (eCRF) but date and value of the corresponding HCV RNA test is missing).

This means only patients who had virological response at their last on-treatment or post-treatment measurement, but had no HCV RNA measurements ≥70 days or >126 days, respectively, post-treatment for reasons not related to safety or effectiveness (e.g. lost-to-follow-up or patient not willing to perform an additional HCV RNA test ≥70 days or >126 days, respectively, post-treatment) will be excluded from this analysis.

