# 4.2.3 Handling of missing data

No data will be imputed for any effectiveness or safety analyses except for the analyses of the HCV RNA endpoints and certain PRO endpoints. The discussion of missing data imputation for the PRO endpoints is included in section 4.2.7.2.3.

HCV RNA values will be selected for an RVR, EOTR and SVR analysis based on visit windows as defined in Table 3. When there is no HCV RNA value in a visit window based on defined visit windows, the closest values before and after the window, regardless of the value chosen for the subsequent and preceding window, will be used for the flanking imputation described below. For analysis of RVR, EOT and SVR, if a subject has a missing HCV RNA value at a post-Day 1 visit but with undetectable or unquantifiable (≤50 IU/mL) HCV RNA levels at both the preceding value and succeeding value, the HCV RNA level will be considered undetectable or unquantifiable,

respectively, at this visit for this subject. In addition, if a subject has an unquantifiable HCV RNA level at the preceding value and an undetectable HCV RNA level at the succeeding value, or vice versa, the HCV RNA level will be imputed as unquantifiable at this visit for this subject.

For analyses of RVR, subjects still missing a value for the visit after flanking imputation will be imputed as a failure. For EoTR and SVR analysis, if there is no value in the appropriate window after flanking imputation but there is an HCV RNA value after the window, then it will be imputed into the EoTR or SVR window respectively. Subsequent to this flanking imputation, if a subject is missing a value for the visit window associated with the analysis, the subject will be imputed as a visit failure (i.e., not undetectable or unquantifiable).

If a subject starts another treatment for HCV, then all HCV RNA values for this subject measured on or after the start date of the new HCV treatment will be excluded from analyses. The subject will be considered a failure for summaries of viral response at all time points after the start of the new HCV treatment.

Due to the non-interventional nature of this study several different methods for determination of the HCV RNA value can be applied. For the purpose of the statistical analysis, a HCV RNA measurement is considered ≤50 IU/mL.

- if a PCR test was used

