# 4.2.7.2 Secondary Variables

# 4.2.7.2.1 Secondary Effectiveness Variables

#### Response

For the other response rates (i.e. RVR, SVR24, EoT response rate, relapse rate, viral breakthrough), the simple percentage of patients and a two-sided 95% confidence interval (CI) of the percentage will be computed (based on the Wilson's score method) as well. The RVR and EoT response rates will be reported for CP and the SVR24 rate will be reported for the respective CPSFU, stratified by genotype and cirrhosis status and overall. The relapse rates will be estimated stratified by SVR window (i.e. during SVR12 window=relapse12, during SVR24

window=relapse24) and stratified by genotype and cirrhosis status and overall in patients of the CP with EoT response who fulfilled the following criteria:

- completed treatment as defined previously.
- had at least one HCV RNA measurement >= 70 days post-treatment or was a treatment failure between EoT and 70 days post-treatment.

Viral breakthrough rates [defined as at least one documented HCV RNA <50 IU/mL followed by HCV RNA ≥50 IU/mL during treatment] will be estimated overall and stratified by genotype and cirrhosis status in all patients of the CP, who have at least one undetectable or unquantifiable, ontreatment HCV RNA measurement and at least one on-treatment or EoT measurement thereafter.

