#### **SVR24 (Exploratory Analyses)**

Univariate and multiple logistic regression (MLR) methods will be used to investigate the impact of various explanatory covariates (patient and disease characteristics) at baseline on SVR24.

These analyses will be of exploratory nature, data driven, and will be performed for CP population. Univariate logistic regression will be performed first and then backward selection procedures will be applied to generate the final MLR model. A p-value <0.05 will be used for the covariates to stay in the model in a backward elimination step. If the percentage of patients with available data for a variable is lower than 80% of the patient group analyzed, then this variable will not be considered in the MLR analysis.

The variables to be considered are as follows:

- · Key demographic information
  - o Age (continuous)
  - o Gender (Female [reference], Male)
  - Race/ethnic origin (White/Caucasian [reference], Black, Asian/Oriental, Other [all other races]); at least two categories with at least 10% of the patients each have to exists, so that this variable will be considered
  - Weight (continuous)
  - o BMI (continuous)
  - IL28B, rs12979860 (CC [reference], CT or TT); patients with unknown genotype are excluded from the respective analyses.
- CHC disease characteristics
  - Years since diagnosis (continuous)
  - Mode of CHC infection (Drug use [reference], Other [all other answers excluding unknown], unknown);
  - Most recent stage of liver fibrosis (No cirrhosis/Transition to cirrhosis [reference],
     Cirrhosis; for definition see 4.2.6.2);
- HCV RNA level at baseline (log10 IU/mL)
- HCV genotype( G1a\*, G1b, G4; for definition see section 4.2.6.2)
- Type of treating institute (Private Practice / Private Hospital, Academic / University Hospital, General Hospital, Other)
- Co-infections (every patient not reporting the respective co-infection is considered as not having the respective co-infection)
  - o HIV(No [reference], Yes)
  - HBV(No [reference], Yes)
- Liver and/or CHC related co-morbidities (every patient not reporting the respective co-morbidity is considered as not having the respective co-morbidity)
  - o Liver transplantation (No [reference], Yes)
  - Steatosis (non-alcoholic) (No [reference], Yes)
  - o Decompensated liver disease (No [reference], Yes)
- Other co-morbidities (every patient not reporting the respective co-morbidity is considered as not having the respective co-morbidity)

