In addition to the summary statistics of the adherence variables, logistic regression analyses will be performed for the following adherence variables: "adherence to Abbvie regimen" in all patients of the CP, "adherence to ribavirin" in all patients of the CP taking RBV, each categorized as follows: >=95%, >80%-<=95%, <=80% to investigate the additional impact of overall treatment adherence on SVR24. The categories may be changed if they are sparsely filled. Adherence will be included as mandatory covariate in addition to the baseline explanatory variables already mentioned above. Also the same methods will be applied as described above.

An overview of Tables is given in Table 8.

Table 8 Overview of Outputs for Primary and Secondary Effectiveness Analysis

Output Title	Output Short Name	Analysis Population
Virological Response Rates by Genotype and Cirrhosis Status – CP/CPSFU - <country></country>	tvr_ <c>_gc_cp</c>	Core population/ Core population with sufficient follow-up data
Virological Response Rates by Genotype and Cirrhosis Status in Patients who Completed ABBVIE Regimen – CP/CPSFU - <country></country>	tvr_ <c>_gc_cp_ARC</c>	Core population/ Core population with sufficient follow-up data: patients who completed ABBVIE regimen
Virological Response Rates - NCP - <country></country>	tvr_ <c>_ncp</c>	Non-core population
Relapse Rates by Genotype and Cirrhosis Status – CP - <country></country>	trr_ <c>_gc_cp</c>	Core population
Viral Breakthrough by Genotype and Cirrhosis Status – CP - <country></country>	tvb_ <c>_gc_cp</c>	Core population
Non-Response Rates by Genotype and Cirrhosis Status – CP - <country></country>	tnrr_ <c>_gc_cp</c>	Core population
Non-Response Rates by Genotype and Cirrhosis Status in Patients who Completed ABBVIE Regimen – CP - <country></country>	tnrr_ <c>_gc_cp_ARC</c>	Core population: patients who completed ABBVIE regimen
Impact of Patient and Disease Characteristics on SVR24 – CP - <country></country>	tis_ <c>_cp</c>	Core population
Adherence by Genotype and Cirrhosis Status - CP - < country>	tah_ <c>_gc_cp</c>	Core population
Adherence by Treatment Regimen and Cirrhosis Status - SP - <country></country>	tah_ <c>_gc_sp</c>	Safety population
Impact of Adherence to AbbVie Regimen on SVR24 - CP - <country></country>	tiaa_ <c>_cp</c>	Core population
Impact of Adherence to Ribavirin on SVR24 in patients taking RBV – CP - <country></country>	tiar_ <c>_cp_RBV</c>	Core population: patients taking RBV

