## 4.2.9 Interim Analyses

One interim analysis is planned. It will be performed in the first quarter of 2017.

All analyses described above will be performed, but the populations will be restricted to patients who started treatment before 1st April 2016 and with a planned treatment duration of 12 weeks.

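### The exploratory SVR24 predictor and adherence models count missing follow-up as failure and start from about as many parameters as virologic non-responders or more, with no test or sparse-data estimator named

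*SAP*

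**What the plan says.** **Selection.** SAP 4.2.7.2.1, SVR24 (Exploratory Analyses), runs univariate logistic regressions of SVR24 on baseline covariates in the CP; "then backward selection procedures will be applied to generate the final MLR model". The retention rule is: "A p-value <0.05 will be used for the covariates to stay in the model in a backward elimination step". Neither the test behind that p-value nor an estimator for sparse data is named; SAP 6 gives only the SAS version. Protocol 9.7.3.3 describes final models "which consider only covariates in the selection procedure with a p-value <0.25 in the corresponding univariate logistic regression analysis". The SAP does not repeat that screen and does not say it is withdrawn.

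**Safeguards.** A variable with less than 80% availability is left out, race needs two categories of at least 10% each, and categories may be merged. For co-infections and co-morbidities, non-report counts as absence.

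**Adherence.** The adherence models use the same methods: "Adherence will be included as mandatory covariate in addition to the baseline explanatory variables already mentioned above". Sparsely filled adherence categories may be changed.

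**Missing SVR24.** Under SAP 4.2.3, if no value is available after flanking values and later values have been tried, "the subject will be imputed as a visit failure". For the descriptive analysis, however, "the SVR24 rate will be reported for the respective CPSFU". The CPSFU leaves out patients whose last HCV RNA showed response and who then have no sufficiently late measurement for reasons unrelated to safety or effectiveness.

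**Interim.** SAP 4.2.9: "All analyses described above will be performed, but the populations will be restricted to patients who started treatment before" a cut-off date, with a planned duration of 12 weeks, so the same models are run in a smaller set.

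**The concern.** Secondary objectives 2 (predictive factors) and 4 (influence of adherence) are served mainly by these models. Two things could distort them.

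- **Outcome.** In the CP a modelled failure is either a virologic failure or a lost sample. A covariate that only predicts who fails to return can look like a predictor of response.
- **Sparse data.** With very few virologic failures per parameter, some covariate patterns will be separated: all carriers of a condition fail, or none does. The ordinary likelihood then has no finite estimate, and what happens next depends on a test the SAP does not name.

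**Working it through.** **Plan's own figures.** Exact Clopper-Pearson widths at 90%/95% are 6.67/4.95 (n=340), 6.47/4.80 (n=360) and 6.29/4.66 (n=380) points. They match SAP Table 1 to within rounding (4.95 against 4.9 stated). The plan gives no event count for the regression models and no SVR24 rate, so the SVR12 planning rates are used as an assumption, with their complement taken as virologic failure.

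**Parameters (SAP 4.2.7.2.1).** Age 1, sex 1, race 3, weight 1, BMI 1, IL28B 1, years since diagnosis 1, mode of infection 2, fibrosis 1, HCV RNA 1, genotype 2, institute 3, ten yes/no co-infections and co-morbidities 10, alcohol 3, ALT 1, AST 1, platelets 1, prior treatment 1, cirrhosis-by-genotype interaction 2. Total 37; without race and IL28B, 37 - 4 = 33.

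**Events per parameter (SAP 3.2).**
- Virologic only: 360 × 0.05 = 18 to 380 × 0.10 = 38. Ratios 18/37 = 0.49 to 38/33 = 1.15.
- With an assumed 5-10% of responders missing and counted as failures: 18 + 0.05 × 342 = 35.1 to 38 + 0.10 × 342 = 72.2. Ratios 35.1/37 = 0.95 to 72.2/33 = 2.19.

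**(a) Share of failures that are missing data.** With virologic failure rate f and missing share m among responders, share = (1-f)m / [f + (1-f)m].

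| | m = 5% | m = 10% |
|---|---|---|
| f = 5% | 0.0475/0.0975 = 49% | 0.095/0.145 = 66% |
| f = 10% | 0.045/0.145 = 31% | 0.09/0.19 = 47% |

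Few patients would be rescued by imputation. Both flanking and the use of a later value need a result after day 210, while planned observation ends at up to 24 weeks (168 days) after treatment, inside the 127-210 day SVR24 window.

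**Spurious odds ratio.** Take a covariate with no effect on virologic failure, but with 20% of carrier responders missing against 5% of others.
- f = 5%: carriers 0.05 + 0.95 × 0.20 = 0.24, others 0.0975; (0.24/0.76)/(0.0975/0.9025) = 2.9.
- f = 10%: carriers 0.28, others 0.145; (0.28/0.72)/(0.145/0.855) = 2.3.
- At 10% against 5% missing: (0.145/0.855)/(0.0975/0.9025) = 1.6 and (0.19/0.81)/(0.145/0.855) = 1.4.

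In simulated backward elimination (covariate in 12% of patients), it was kept in 71%/56% of CP models at 5%/10% failure and in 5%/3% of CPSFU models for SVR24. At 10% against 5% missing the figures were 14%/11% and 2%/2%.

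**(b) Separation in a 2×2 table.** 360 patients, 18 failures, 5 carriers.
- 4 of 5 carriers fail: Wald p < 0.001, likelihood-ratio p = 8 × 10⁻⁶. Both keep the covariate.
- 5 of 5 fail: the estimate is infinite; Wald p = 0.93 (its exact value depends on where the iteration stops), likelihood-ratio p = 2 × 10⁻⁸.
- 5 of 5 under Firth, which in this table adds ½ to each cell: odds ratio (5.5 × 342.5)/(0.5 × 13.5) = 279, finite. The penalised log-likelihoods are -59.14 with the covariate and -74.49 without; the statistic is 2 × 15.35 = 30.7, p = 3 × 10⁻⁸.

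**How often all 7 carriers fail** (2% of about 370 patients). Failure odds for a carrier = f/(1-f) × exp(log-odds).

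| Log-odds | f = 5% | f = 10% |
|---|---|---|
| 2.5 | 0.391⁷ = 0.1% | 0.575⁷ = 2% |
| 3.5 | 0.635⁷ = 4% | 0.786⁷ = 19% |
| 4.5 | 0.826⁷ = 26% | 0.909⁷ = 51% |

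**Simulated retention of one true predictor** (N = 370, 33 parameters, 2% prevalence, f = 5%/10%).

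| Log-odds | Ordinary Wald | Wald after p<0.25 screen | Firth |
|---|---|---|---|
| 4.5 | 65%/48% | 69%/49% | 100%/100% |
| 3.5 | 91%/77% | 92%/78% | 98%/99% |
| 2.5 | 78%/83% | not given | 81%/88% |

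At 5% prevalence and log-odds 4.5 the contrast shrinks to 95%/80% against 100%/100%. The ordinary likelihood-ratio test at log-odds 3.5-4.5 kept the predictor in 97-100% of runs (4.5 at 10% failure was not run), but 41-53% of final models held a coefficient above 8 in absolute value; Firth had none. The elimination test behind the Firth column is not recorded, so the 2×2 result above is the direct check on the penalised likelihood-ratio test.

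**The case against.** A reader might infer that the procedure will generally discard strong rare predictors. The documents do not support that. Loss needs separation and a Wald test, and the SAP does not specify Wald. It also needs effects beyond those reported: in the phase III cirrhosis study in Protocol 7.1, the worst subgroup has 80% SVR against 92-96% overall. That is an odds ratio for failure of (0.20/0.80)/(0.08/0.92) = 2.9 to (0.20/0.80)/(0.04/0.96) = 6.0, or log-odds 1.1-1.8. At log-odds 2.5 the methods hardly differ. This limits the point but does not remove it: the likelihood-ratio route still leaves an unbounded odds ratio to report.

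A reader might also take 0.5-1.2 as the ratio in the model actually fitted. It counts virologic failures only; missing-as-failure raises it, by adding events that are not virologic.

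Nor is separation in the adherence models beyond remedy because the term is mandatory. Merging a sparse category into one with both outcomes removes it. Merging cannot help a yes/no co-morbidity, and the 80% rule cannot either, since non-report counts as absence.

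Missing-as-failure is pre-specified, and Protocol 9.9 acknowledges that missing data can understate the SVR rate. SAP 4.2.7.2.1 also splits SVR12 non-response by cause. That stands, but no such split is planned for SVR24, the outcome modelled. The CPSFU is not neutral either: it drops patients lost after a response, including unobserved relapsers, and the simulation put missingness only in responders, which favours it.

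Finally, the analysis is labelled exploratory and drives no decision.

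**Conclusion.** The point holds in limited form, as a correctable weakness of exploratory models that serve secondary objectives 2 and 4.

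- **Outcome.** With 5-10% of responders missing, 31-66% of modelled failures are missing data. A purely follow-up-related covariate gets an odds ratio of 2.3-2.9 if missingness is 20% against 5%, and only 1.4-1.6 at 10% against 5%.
- **Sparse data.** There are 0.5-1.2 virologic non-responders per parameter, or 0.95-2.2 events when missing data are included. The harm from separation is confined to very strong effects in rare yes/no conditions; elsewhere the choice of estimator makes little difference.

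Missing shares, prevalences and effect sizes are assumptions; neither document gives them. The omitted p<0.25 screen is a matter of consistency between the documents: in the simulation it barely changed the loss.

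**What to change.** In SAP 4.2.7.2.1, for the SVR24 predictor models and the adherence models, and for their interim run:

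1. Repeat the models in the CPSFU for SVR24 as a sensitivity analysis, noting that this population drops patients lost after a response and so is not free of bias.
2. Report the SVR24 non-responders in each model split into virologic failure and missing data, as is already planned for SVR12.
3. Fit the models by Firth-penalised likelihood with profile-likelihood intervals, and eliminate on the penalised likelihood-ratio test at p<0.05.
4. State whether the protocol's univariate p<0.25 screen applies; if not, declare the departure.

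The cost is SAP wording, one count table, one repeat run and a little more programming. Odds ratios will be slightly shrunken. Firth fitting does not cure the multiplicity of stepwise selection, so selected covariates still need to be read as exploratory.
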